1.3 Schedule of Activities (SoA)

Study Period	Screening	Baseline / Randomization	Intervention				Follow-up TC ^a	Disc ^c	Notes
			TC	TC	3	4			
Visit	1	2	TC	TC	3	4	-	NA	
Scheduled Day	-14 to -1	1	7	21	42	84	98	NA	
Scheduling Window (recommended)	NA	NA	+3 days	±3 days	±4 days	±4 days	+7 days	NA	
Scheduled Week	-2 to -1	-	1	3	6	12	14	NA	
Administrative Procedures									
Informed Consent	X								
Informed Consent for FBR	X								FBR is optional for the participant.
Participant Identification Card	X	X							Update with allocation number once randomized.
Inclusion/Exclusion Criteria	X	X							
Demographics, Medical History	X								
Prior/Concomitant Medication Review	X	X	X	X	X	X	X	X	
Randomization		X							
Gefapixant/Placebo Administration/Dispensing		X			X				
Study Intervention Accountability					X	X		X	
Contact IRT System	X	X			X	X		X	
Efficacy Procedures									
Activate ePROs	X	X			X	X		X	See ePRO vendor manual.
Issue/instruct on use of e-Diary	X								
Review e-Diary compliance and instructions for use		X	X	X	X	X		X	Disc: Only when participant discontinues from study intervention (not discontinues from study).
Deactivate/collect e-Diary						X		X	Disc: Only when participant discontinues from study (not just discontinues study intervention).

Study Period	Screening	Baseline / Randomization	Intervention				Follow-up TC ^a	Disc ^c	Notes
			TC	TC	3	4			
Visit	1	2	TC	TC	3	4	-	NA	
Scheduled Day	-14 to -1	1	7	21	42	84	98	NA	
Scheduling Window (recommended)	NA	NA	+3 days	±3 days	±4 days	±4 days	+7 days	NA	
Scheduled Week	-2 to -1	-	1	3	6	12	14	NA	
LCQ		X			X	X		X	Complete at clinic visit: - Visit 2: After confirming eligibility for randomization and before first dose of study intervention. - Visits 3 & 4/Disc: Before all other procedures.
CSD	Complete daily (in evening)								Remind participant of need to complete daily.
Cough Severity VAS	Complete at Visit 1 clinic visit and daily (in evening)								Visits 2 & 3: Remind participant of need to complete daily.
PGIC						X		X	Complete at clinic visit.
WPAI		X				X		X	Visit 2: Complete at clinic visit before first dose of study intervention.
Safety Procedures									
Chest Radiograph or CT Thorax	X								Not required if done in the past 1 year and after onset of chronic cough.
Physical examination	X					X		X	Visit 1 (Screening): full examination. Visit 4 and Disc: directed examination.
Height	X								
Weight	X					X		X	
Vital Signs	X	X			X	X		X	
12-lead ECG	X								
Spirometry	X								

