7 DISCONTINUATION OF STUDY INTERVENTION AND PARTICIPANT WITHDRAWAL

7.1 Discontinuation of Study Intervention

Discontinuation of study intervention does not represent withdrawal from the study.

As certain data on clinical events beyond study intervention discontinuation may be important to the study, they must be collected through the participant's last scheduled follow-up, even if the participant has discontinued study intervention. Therefore, all participants who discontinue study intervention prior to completion of the protocol-specified treatment period will still continue to participate in the study as specified in Section 1.3.

Participants may discontinue study intervention at any time for any reason or be discontinued from the study intervention at the discretion of the investigator should any untoward effect occur. In addition, a participant may be discontinued from study intervention by the investigator or the Sponsor if study intervention is inappropriate, the study plan is violated, or for administrative and/or other safety reasons. Specific details regarding procedures to be performed at study intervention discontinuation are provided in Section 8.1.9.

A participant must be discontinued from study intervention but continue to be monitored in the study for any of the following reasons:

- The participant or participant's legally acceptable representative requests to discontinue study intervention.
- The participant's treatment assignment has been unblinded by the investigator, MSD subsidiary, or through the emergency unblinding call center.
- The participant has a medical condition or personal circumstance which, in the opinion of the investigator and/or Sponsor, placed the participant at unnecessary risk from continued administration of study intervention.
- The participant has a confirmed positive serum pregnancy test.
- In case of clinically significant and potentially drug-related rash or signs and/or symptoms consistent with allergic drug reaction or anaphylaxis to study intervention.
- Chronic failure to comply with the dosing, evaluations, or other requirements of the study, despite documentation at the site of repeated efforts to reinforce compliance.

For participants who discontinue study intervention early, refer to Section 8.10.3.

Discontinuation from study intervention is “permanent.” Once a participant is discontinued, he/she shall not be allowed to restart study intervention.

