8.1.9 Discontinuation and Withdrawal

Participants who discontinue study intervention prior to completion of the intervention period should be encouraged to continue to be followed for all remaining study visits as outlined in the SoA (Section 1.3 and Section 8.10.3).

When a participant withdraws from participation in the study, all applicable activities scheduled for the Discontinuation Visit should be performed (at the time of withdrawal). Any AEs that are present at the time of withdrawal should be followed in accordance with the safety requirements outlined in Section 8.3.

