8.10.3 Discontinued Participants Continuing to be Monitored in the Study

It is intended that all participants should be followed throughout the study, regardless of premature discontinuation of intervention, unless the participant withdraws consent. Thus, participants who discontinue from study intervention prior to completion of the study should continue to be monitored to obtain relevant information through the end of the study.

If a participant is discontinued from the study intervention early:

- the Discontinuation Visit should be performed as soon as possible; Procedures, including the e-Diary assessments, should be performed as outlined for the Discontinuation Visit in the SoA (Section 1.3).

Note: If a participant discontinues at a regularly scheduled study visit, the procedures outlined for the Discontinuation Visit in the SoA should be followed in place of the procedures for the regularly scheduled study visit.

- a safety follow-up telephone call should be conducted a minimum of 14 days (with an allowed variance of up to +7 days) after the last dose of study intervention; and
- Study site visits should continue to be performed at timepoints that correspond to each remaining study visit. These visits will allow collection of follow-up information, limited to:
 - AEs;
 - Concomitant medication use; and
 - e-Diary assessments, as outlined in the SoA (Section 1.3).

Note: If the participant discontinues study intervention at a regularly scheduled study visit but remains in the study, the Discontinuation Visit should be performed, and the regularly scheduled study visits should resume thereafter. For example: If a participant discontinues study intervention at the time of Visit 3, procedures for the Discontinuation Visit should be performed at that time. The next expected study visit would be Visit 4.

Concomitant therapies specifically prohibited (Section 6.5) while the participant was on study intervention are no longer prohibited after discontinuation of study intervention.

- For these participants who have discontinued study intervention early, sites will be instructed to exert diligent efforts to continue to contact them. To enable sites to reach participants, the participants should provide primary and secondary contact information (eg, home telephone, work telephone, mobile telephone). Sites must document the outcome of the telephone contact(s), to demonstrate diligent efforts have been made.

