9.11 Compliance (Medication Adherence)

For each participant, percent compliance will be calculated using the following formula:

$$\text{Percent Compliance} = \frac{\text{Number of Days on Therapy}}{\text{Number of Days Expected on Therapy}} \times 100\%$$

A day within the study will be considered an “on-therapy” day if the participant takes all required intervention as instructed in Section 8. When a participant takes less than or more than the required intervention on a day, that day is not considered an on-therapy day.

For participants who are followed for the entire study period, the “Number of Days Should be on Therapy” is the total number of days from the first scheduled intervention day to the last scheduled intervention day. For participants who discontinue from the study permanently, the “Number of Days Should Be on Therapy” is the total number of days from the first scheduled intervention day to the last dose day.

Summary statistics will be provided on percent compliance by intervention group for the APaT population.

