3.11 COMPLIANCE (MEDICATION ADHERENCE)

For each participant, percent compliance will be calculated using the following formula:

$$\text{Percent Compliance} = \frac{\text{Number of Days on Therapy}}{\text{Number of Days Expected on Therapy}} \times 100\%$$

A day within the study will be considered an “on-therapy” day if the participant takes all required intervention as instructed in Section 8. When a participant takes less than or more than the required intervention on a day, that day is not considered an on-therapy day.

For participants who are followed for the entire study period, the “Number of Days Should be on Therapy” is the total number of days from the first scheduled intervention day to the last scheduled intervention day. For participants who discontinue from the study permanently, the “Number of Days Should Be on Therapy” is the total number of days from the first scheduled intervention day to the last dose day.

Summary statistics will be provided on percent compliance by intervention group for the APaT population.

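### As written, the percent-compliance denominator depends on leaving the study, not on stopping drug: full dosing to Day 21 scores about 25% for a participant who stays in follow-up and 100% for one who leaves

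*Combined protocol and SAP*

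**What the plan says.** Protocol 9.11 defines percent compliance as days on therapy divided by the "Number of Days Expected on Therapy", times 100. A day counts in the numerator only if exactly the required study intervention was taken.

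The denominator has two rules:

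- "For participants who are followed for the entire study period", it runs from the first to the last scheduled intervention day.
- "For participants who discontinue from the study permanently", it "is the total number of days from the first scheduled intervention day to the last dose day".

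The text that states these rules gives the denominator a different name from the one in the formula. sSAP 3.11 repeats the section with the same wording. The result is summarised by intervention group in the APaT population.

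Other sections treat drug status and study status as separate. Protocol 7.1 states: "Discontinuation of study intervention does not represent withdrawal from the study". It also makes stopping drug permanent, with no restart. Section 8.1.9 says that participants who stop drug early "should be encouraged to continue to be followed for all remaining study visits". Section 8.10.3 adds: "It is intended that all participants should be followed throughout the study, regardless of premature discontinuation of intervention, unless the participant withdraws consent". The e-Diary notes in the Schedule of Activities (1.3) also distinguish the two statuses.

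**The concern.** Neither rule is triggered by stopping drug. A participant who stops early and stays to the end falls under the first rule, so days on which no drug was due count against them. A participant with the same dosing who leaves falls under the second rule, and those days do not count. Because drug cannot be restarted, each day after the stop enlarges the stayer's denominator and can never add to the numerator.

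The participants affected are the ones the protocol asks sites to keep in follow-up. The by-arm summary therefore mixes adherence while on drug with early stopping, and the mix depends on retention. Someone who stops at Day 21, stays some weeks and then withdraws moves from the first rule to the second, and the score changes with no change in drug-taking.

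The stake is how a descriptive table is read. No hypothesis test depends on it.

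**Working it through.** The plan states no compliance figure to reproduce, so the formula in 9.11 is applied directly.

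**Inputs**

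- Last scheduled dose: the evening before Visit 4 (8.1.8). Visit 4 is on Day 84 with a window of ±4 days (1.3).
- Scheduled days D: 84 − 1 = 83. Across the window, 80 − 1 = 79 to 88 − 1 = 87. Section 8.1.8.1 gives approximately 84 days, so D = 84 is also shown.
- Planned arm size: 207 (9.9).
- Assumptions: every day up to the stop day d counts as on therapy. The stop days are illustrative.

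**Formulas**

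- Stays in follow-up: 100 × d/D
- Leaves the study: 100 × d/d = 100%
- Fall in arm mean per stayer, in points: (100 − 100 × d/83)/207

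| Stop day d | Stays, D = 83 | D = 87 to D = 79 | D = 84 | Leaves | Fall in arm mean per stayer |
|---|---|---|---|---|---|
| 21 | 21/83 = 25.3% | 24.1% to 26.6% | 25.0% | 100% | 74.7/207 = 0.36 |
| 42 | 42/83 = 50.6% | 48.3% to 53.2% | 50.0% | 100% | 49.4/207 = 0.24 |
| 63 | 63/83 = 75.9% | 72.4% to 79.7% | 75.0% | 100% | 24.1/207 = 0.12 |

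**Day 1 convention.** If the first dose is taken in the evening and Day 1 does not count as on therapy, the Day 21 contrast with D = 84 is 20/84 = 23.8% against 20/21 = 95.2%. The gap remains.

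**Reversal of order.** A participant with 11 full-dose days up to a last dose on Day 21, who then leaves, scores 11/21 = 52.4%. That is above the 25.3% for a participant who took every dose on all 21 days and stayed.

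**Under the proposed rule.** The Day 21 stopper scores 21/21 = 100% whether they stay or leave, and the 11-of-21 participant scores 52.4% either way. The order is then correct.

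**The case against.** The strongest objection is that the authors probably meant discontinuation of study intervention. The shorter denominator ends at the last dose, not at study exit. Protocol 4.1 and 9.7.1 also set completing the study against stopping drug early as though these were the only two outcomes, and sSAP 4.1 speaks loosely of discontinuation from the trial. This is plausible. But neither document states that intention in the compliance section, and two programmers could reasonably code different status variables.

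A second reading is that no therapy is expected or scheduled after a permanent stop, so the first rule already ends there. That would make the separate last-dose-day rule for leavers redundant, which counts against it.

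Third, the measure is descriptive, and discontinuation and exposure are summarised separately, so a reader can see early stopping elsewhere. This stands, and it is why the point ranks low. The between-visit compliance check in 6.4 is a separate process. The list of protocol violation criteria in sSAP 3.5.1 cannot be seen in the text available, so nothing here rests on whether compliance enters it.

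Fourth, the stop days and the 11-of-21 case are constructed. That is true. They show how the rule behaves and do not predict what the trial will find.

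Fifth, running the denominator to the last scheduled day for everyone would also remove the dependence on study status. It would, but it measures the share of planned treatment taken. The last-dose-day rule is already in 9.11, and extending it keeps the measure about adherence while on drug.

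**Conclusion.** The concern holds for the rule as written. Identical dosing to Day 21 gives 25.3% (24.1% to 26.6% over the Visit 4 window) for a participant who stays and 100% for one who leaves. The contrast shrinks with later stopping, to 75.9% against 100% at Day 63. Each stayer lowers the arm mean by 0.36, 0.24 or 0.12 points for a stop at Day 21, 42 or 63, assuming full dosing until the stop and 207 per arm.

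The documents give no by-arm rates of stopping drug or of staying in follow-up, so no arm total and no difference between arms is claimed. The effect is limited to the descriptive APaT compliance summary; the primary test, power and adverse-event proportions are untouched. This is a low-priority correction. If drug status was always intended, the change simply records it.

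**What to change.** In protocol 9.11 and sSAP 3.11:

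1. For anyone who permanently discontinues study intervention, end the denominator at the last dose day, whether or not they remain in the study. For everyone else, end it at the last scheduled intervention day.
2. Define the last scheduled intervention day for this calculation, because 8.1.8 (evening before Visit 4) and 8.1.8.1 (approximately 84 days) differ slightly.
3. Use one name for the denominator.

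Two clarifications could be made in the same edit. Protocol 9.12 and sSAP 3.12 should say whether days on therapy, as the measure of exposure, follows the all-tablets rule of 9.11 or the time from first to last dose. The plan should also say whether a day with a dose skipped under 8.1.8.1 counts as on therapy.

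The cost is wording and one derivation rule in two places. No new data item is needed. The current rule already requires the last dose day for leavers, 8.6.1 puts the last dose before the pharmacokinetic sample in the eCRF, and 8.10.3 times the safety call from the last dose. Discontinuation is already summarised (9.6.2, 9.6.3.1 and the matching sSAP sections), so nothing needs adding there.

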9.12 Extent of Exposure

The duration of intervention for each participant will be evaluated by calculating the number of days on therapy. Exposure to study intervention will be summarized using descriptive statistics (mean, SD, median, minimum, and maximum) for the APaT population.

10 SUPPORTING DOCUMENTATION AND OPERATIONAL CONSIDERATIONS

10.1 Appendix 1: Regulatory, Ethical, and Study Oversight Considerations

10.1.1 Code of Conduct for Clinical Trials

Merck Sharp and Dohme Corp., a subsidiary of Merck & Co., Inc. (MSD)

Code of Conduct for Interventional Clinical Trials

I. Introduction

A. Purpose

MSD, through its subsidiaries, conducts clinical trials worldwide to evaluate the safety and effectiveness of our products. As such, we are committed to designing, implementing, conducting, analyzing, and reporting these trials in compliance with the highest ethical and scientific standards. Protection of participants in clinical trials is the overriding concern in the design and conduct of clinical trials. In all cases, MSD clinical trials will be conducted in compliance with local and/or national regulations, and International Council for Harmonisation Good Clinical Practice (ICH-GCP), and also in accordance with the ethical principles that have their origin in the Declaration of Helsinki.

B. Scope

Highest ethical and scientific standards shall be endorsed for all clinical interventional investigations sponsored by MSD irrespective of the party (parties) employed for their execution (e.g., contract research organizations, collaborative research efforts). This Code is not intended to apply to trials that are observational in nature, or which are retrospective. Further, this Code does not apply to investigator-initiated trials, which are not under the full control of MSD.

II. Scientific Issues

A. Trial Conduct

1. Trial Design

Except for pilot or estimation trials, clinical trial protocols will be hypothesis-driven to assess safety, efficacy and/or pharmacokinetic or pharmacodynamic indices of MSD or comparator products. Alternatively, MSD may conduct outcomes research trials, trials to assess or validate various endpoint measures, or trials to determine patient preferences, etc.

The design (i.e., participant population, duration, statistical power) must be adequate to address the specific purpose of the trial. Participants must meet protocol entry criteria to be enrolled in the trial.

2. Site Selection

MSD selects investigative sites based on medical expertise, access to appropriate participants, adequacy of facilities and staff, previous performance in clinical trials, as well as budgetary considerations. Prior to trial initiation, sites are evaluated by MSD personnel (or individuals acting on behalf of MSD) to assess the ability to successfully conduct the trial.

3. Site Monitoring/Scientific Integrity

Investigative trial sites are monitored to assess compliance with the trial protocol and Good Clinical Practice (GCP). MSD reviews clinical data for accuracy, completeness, and consistency. Data are verified versus source documentation according to standard operating procedures. Per MSD policies and procedures, if fraud,

scientific/research misconduct or serious GCP-non-compliance is suspected, the issues are investigated. When necessary, the clinical site will be closed, the responsible regulatory authorities and ethics review committees notified.

B. Publication and Authorship

Regardless of trial outcome, MSD commits to publish the primary and secondary results of its registered trials of marketed products in which treatment is assigned, according to the pre-specified plans for data analysis. To the extent scientifically appropriate, MSD seeks to publish the results of other analyses it conducts that are important to patients, physicians, and payers. Some early phase or pilot trials are intended to be hypothesis-generating rather than hypothesis testing; in such cases, publication of results may not be appropriate since the trial may be underpowered and the analyses complicated by statistical issues such as multiplicity.

MSD's policy on authorship is consistent with the recommendations published by the International Committee of Medical Journal Editors (ICMJE). In summary, authorship should reflect significant contribution to the design and conduct of the trial, performance or interpretation of the analysis, and/or writing of the manuscript. All named authors must be able to defend the trial results and conclusions. MSD funding of a trial will be acknowledged in publications.

III. Participant Protection

A. Regulatory Authority and Ethics Committee Review (Institutional Review Board [IRB]/Independent Ethics Committee [IEC])

All protocols and protocol amendments will be submitted by MSD for regulatory authority acceptance/authorization prior to implementation of the trial or amendment, in compliance with local and/or national regulations.

The protocol, protocol amendment(s), informed consent form, investigator's brochure, and other relevant trial documents must be reviewed and approved by an IRB/IEC before being implemented at each site, in compliance with local and/or national regulations. Changes to the protocol that are required urgently to eliminate an immediate hazard and to protect participant safety may be enacted in anticipation of ethics committee approval. MSD will inform regulatory authorities of such new measures to protect participant safety, in compliance with local and/or national regulations.

B. Safety

The guiding principle in decision-making in clinical trials is that participant welfare is of primary importance. Potential participants will be informed of the risks and benefits of, as well as alternatives to, trial participation. At a minimum, trial designs will take into account the local standard of care.

All participation in MSD clinical trials is voluntary. Participants enter the trial only after informed consent is obtained. Participants may withdraw from an MSD trial at any time, without any influence on their access to, or receipt of, medical care that may otherwise be available to them.

C. Confidentiality

MSD is committed to safeguarding participant confidentiality, to the greatest extent possible. Unless required by law, only the investigator, Sponsor (or individuals acting on behalf of MSD), ethics committee, and/or regulatory authorities will have access to confidential medical records that might identify the participant by name.

D. Genomic Research

Genomic research will only be conducted in accordance with a protocol and informed consent authorized by an ethics committee.

IV. Financial Considerations

A. Payments to Investigators

Clinical trials are time- and labor-intensive. It is MSD's policy to compensate investigators (or the sponsoring institution) in a fair manner for the work performed in support of MSD trials. MSD does not pay incentives to enroll participants in its trials. However, when enrollment is particularly challenging, additional payments may be made to compensate for the time spent in extra recruiting efforts.

MSD does not pay for participant referrals. However, MSD may compensate referring physicians for time spent on chart review and medical evaluation to identify potentially eligible participants.

B. Clinical Research Funding

Informed consent forms will disclose that the trial is sponsored by MSD, and that the investigator or sponsoring institution is being paid or provided a grant for performing the trial. However, the local ethics committee may wish to alter the wording of the disclosure statement to be consistent with financial practices at that institution. As noted above, all publications resulting from MSD trials will indicate MSD as a source of funding.

C. Funding for Travel and Other Requests

Funding of travel by investigators and support staff (e.g., to scientific meetings, investigator meetings, etc.) will be consistent with local guidelines and practices.

V. Investigator Commitment

Investigators will be expected to review MSD's Code of Conduct as an appendix to the trial protocol, and in signing the protocol, agree to support these ethical and scientific standards.

